#### 6.3.3.4 Medication Days per Month on Non-Scheduled Days in the OLE Phase

This adhoc analysis was added to the CSR and further modified for the Addendum Report.

See Section 7.6.2.3 for the definition of non-scheduled days in the OLE phase.

Rescue medication is defined as triptan, ergotamine, or other medication (see Section 6.3.2.2). On non-scheduled days, either OL rimegepant or rescue medication can be taken.

For a given medication, the number of medication days per month on non-scheduled days for the overall OL rimegepant mean is defined as:  $28 \times (\text{total number of medication days on the same days as non-scheduled days through Month 13 in the on-OL rimegepant efficacy analysis period}) / (\text{total number of non-scheduled days through Month 13 in the on-OL rimegepant efficacy analysis period})$ .

The number of medication days per month on non-scheduled days for the overall OL mean will be summarized descriptively as a continuous parameter for evaluable OL rimegepant mITT subjects by treatment group and overall for the following medications:

- Any medication: rimegepant or rescue medication
  - Acute migraine medication, defined as rimegepant, triptan, or ergotamine
  - Rimegepant only
  - Rescue medication only
  - Rimegepant and rescue medication
  - Triptan or ergotamine only.
-

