2.1 Primary

- To compare the efficacy of rimegepant to placebo as a preventive treatment for migraine, as measured by the reduction from baseline in the mean number of migraine days per month in the last four weeks of the double-blind treatment phase. (A month is defined as 4 weeks for the purpose of this protocol).

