## 1.2 Study Objectives

### 1.2.1 Primary Objectives

To compare the efficacy of rimegepant to placebo as a preventive treatment for migraine, as measured by the reduction from baseline in the mean number of migraine days per month in the last 4 weeks of the DBT phase (a month is defined as 4 weeks for the purpose of this protocol).

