### 7.6.2.3 *Scheduled and Non-Scheduled Days in the OLE Phase*

All days in the on-OL rimegepant efficacy analysis period are classified as either scheduled or non-scheduled days. Scheduled days are defined as days in the planned EOD dosing schedule. All other days are considered to be non-scheduled days.

For each OL rimegepant treated subject, the initial planned EOD dosing schedule pattern is classified as even or odd with respect to the OL rimegepant start date as follows:

- Calculate planned OL rimegepant day = scheduled report date – OL rimegepant start date for each scheduled report date in the on-OL rimegepant efficacy analysis period.

- A scheduled report date is a complete eDiary finding date from a “yes” response to either (1) question about having already taken study medication today to treat headache from the scheduled dosing report, or (2) question about taking a scheduled dose of study medication today from the scheduled dosing report.
- If the first planned OL rimegepant day is an even number or missing, then the initial planned EOD dosing schedule pattern is even.
- If the first planned OL rimegepant day is an odd number, then the initial planned EOD dosing schedule pattern is odd.

It is expected that scheduled days follow the initial planned EOD dosing schedule for the entire OLE phase. Thus, if the initial planned EOD dosing schedule pattern is even, then it is expected that scheduled days are all even planned OL rimegepant days 0, 2, 4, etc. Otherwise, if the initial planned EOD dosing schedule pattern is odd, then it is expected that scheduled days are all odd planned OL rimegepant days 1, 3, 5, etc.

However, in rare cases, the eDiary may reset at scheduled report dates and switch planned EOD dosing schedule patterns. For example, the planned EOD dosing schedule may start as even, switch to odd, and then switch back to even. A switch date is defined as a scheduled report date with an odd number of days between it and the previous scheduled report date. Switch dates define blocks of days within the on-OL rimegepant efficacy analysis period as follows:

- Block 1: All days in the OL rimegepant efficacy analysis period before the first switch are considered to follow the initial planned EOD dosing pattern.

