- Block 2: All days on or after the first switch but before the second switch are considered to follow the second planned EOD dosing pattern. If there is only 1 switch, then all days on or after the first switch are considered to follow the second planned EOD dosing pattern.
- Block 3: All days on or after the second switch but before the third switch are considered to follow the initial planned EOD dosing pattern. If there are only 2 switches, then all days on or after the second switch are considered to follow the initial planned EOD dosing pattern.

This iterative process continues as needed.

Example:

- Subject has 26 days in the on-OL rimegepant efficacy analysis period, i.e., OL rimegepant start date on day 0 and OL rimegepant last date + 1 on day 25.
  - Scheduled report dates fall on planned OL rimegepant days 0, 2, 4, 8, 9, 11, 15, 18, 22, and 24.
    - The initial EOD dosing schedule pattern is even.
    - There are 2 switches: day 9 is the first switch and day 18 is the second switch.
    - All even days from 0 to 8 inclusive (i.e., days 0, 2, 4, 6, 8) are scheduled days.
    - All odd days from 9 to 17 inclusive (i.e., days 9, 11, 13, 15, 17) are scheduled days.
    - All even days from 18 to 24 inclusive (i.e., 18, 20, 22, 24) are scheduled days.
-

- All other days (i.e., days 1, 3, 5, 7, 10, 12, 14, 16, 19, 21, 23, and 25) are non-scheduled days.

Note that (1) imputed OL rimegepant dates and (2) OL rimegepant dates from the scheduled dosing report can only be on scheduled days. OL rimegepant dates from the evening report headache log, follow-up headache log, or medication reconciliation form can be on scheduled or non-scheduled days.

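### SAP 6.3.3.4 labels as days per month a rate per 28 non-scheduled days, so all six rows read about twice the rate per 28 calendar days

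*SAP*

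**What the plan says.** SAP 6.3.3.4 covers six medication categories in the open-label extension (OLE): any medication, acute migraine medication, rimegepant only, rescue only, rimegepant and rescue, and triptan or ergotamine only. For each, "the number of medication days per month on non-scheduled days for the overall OL rimegepant mean is defined as" 28 times a ratio. The numerator is the "total number of medication days on the same days as non-scheduled days through Month 13 in the on-OL rimegepant efficacy analysis period"; the denominator is the "total number of non-scheduled days through Month 13 in the on-OL rimegepant efficacy analysis period".

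SAP 7.6.2.3 fixes what counts as non-scheduled: "All days in the on-OL rimegepant efficacy analysis period are classified as either scheduled or non-scheduled days", and "Scheduled days are defined as days in the planned EOD dosing schedule". Non-scheduled days are the remainder. Its 26-day example ends: "All other days (i.e., days 1, 3, 5, 7, 10, 12, 14, 16, 19, 21, 23, and 25) are non-scheduled days".

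On the unit, SAP 1.2.1 says that "a month is defined as 4 weeks for the purpose of this protocol", and Protocol 2.1 says the same.

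Section 6.3.3.4 describes the table as an ad hoc analysis added to the CSR and modified for the Addendum Report. It does not say that a month has another meaning there, and it gives no reason for the choice of denominator.

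**The concern.** The table is meant to show how often subjects on open-label treatment add rimegepant, triptans or other rescue on days between scheduled doses. A reader who sees days per month will take the unit to be 28 calendar days, as the documents define it and as the SAP uses it elsewhere. On that reading the table overstates off-day use by a factor of about 2.

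The other monthly diary measures do not have this feature. For the OLE phase, migraine days (SAP 6.3.1.2), rescue medication days (6.3.2.2) and triptan or ergotamine days (6.3.3.3) are all 28 times a count divided by efficacy data days. The closest parallel is menstrually-related migraine days (6.3.3.1). Its numerator is also restricted to a subset of days, those in a menstrual interval, yet its denominator is all efficacy data days.

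The table would also fail to reconcile with exposure, which is in tablets per 4 calendar weeks with subgroup cuts at 14 and 16 (SAP 6.1.3.4 and 6.2.6.1). A subject who takes 14 scheduled tablets and 2 off-day tablets per 28 days averages 16 tablets per month, but would show about 4 off-day rimegepant days per month here.

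**Working it through.** **Notation.** m = medication days on non-scheduled days; NS = non-scheduled days; D = all days in the open-label efficacy period through Month 13; E = efficacy data days in that period.

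**Step 1: reproduce the SAP's own example (7.6.2.3).** Scheduled reports fall on days 0, 2, 4, 8, 9, 11, 15, 18, 22 and 24. Odd gaps occur at 8 to 9 and 15 to 18, so the pattern switches on days 9 and 18. Scheduled days are then 0, 2, 4, 6, 8 (five), 9, 11, 13, 15, 17 (five) and 18, 20, 22, 24 (four), 14 in all. The other 26 − 14 = 12 days are non-scheduled. This matches the SAP.

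**Step 2: compare the formula with a calendar-month rate.**
- SAP formula: 28 × m / NS
- Rate per 28 calendar days: 28 × m / D
- Ratio of the two: D / NS, which does not depend on m or on the medication category

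Strict every-other-day dosing: D / NS = 28/14 = 364/182 = 2.00. SAP example: 26/12 = 2.17. The example is short and built to show schedule switching, which the SAP calls rare, so 2.0 is the representative value.

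**Step 3: effect on reported values, strict every-other-day dosing.**

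| Off-day use per 28 calendar days | SAP 6.3.3.4 result |
|---|---|
| 1 | 2 |
| 2 | 4 |
| 4 | 8 |
| 7 | 14 |
| 14 (every off-day) | 28 |

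As an assumed subject, take 26 off-day medication days over 52 weeks (D = 364, NS = 182). The SAP gives 28 × 26/182 = 4.0; the calendar rate is 28 × 26/364 = 2.0.

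**Step 4: compare with a rate per efficacy data day.** The sibling measures use 28 × m / E. If a share c of days has efficacy data, E = c × D, and the ratio becomes E / NS = 2c under strict every-other-day dosing. The documents give no value for c, so a range is assumed:

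| Assumed completeness c | SAP result ÷ efficacy-data-day rate |
|---|---|
| 100% | 2.0 |
| 90% | 1.8 |
| 80% | 1.6 |
| 70% | 1.4 |

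The factor falls because non-scheduled days without diary data stay in the SAP denominator and count as days without use.

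**Step 5: is m contained in E?** A rescue medication day must be a day of efficacy data (SAP 6.3.2.2). An open-label rimegepant date on a non-scheduled day is itself an efficacy date (SAP 7.3). So E is a valid denominator for all six rows.

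**The case against.** The strongest defence is that this is a labelling problem and not a faulty calculation. The table title names non-scheduled days, numerator and denominator are restricted to the same set of days, and both are written out in full. As a rate standardised to 28 non-scheduled days the quantity is coherent. The table templates are in separate mock documents that are not available here, and a footnote there may state the unit. What stands is that the ratio is usable once correctly named. What does not stand is the name: the SAP defines a month as 4 weeks, does not redefine it in 6.3.3.4, and an unseen footnote cannot be assumed to do so.

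The second defence concerns weight, and it stands. The analysis is ad hoc and descriptive, has no matching objective or estimand, and produces no test. The factor is nearly the same for every subject and both groups, so ratios between groups hardly move, although absolute levels and differences scale with it.

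Three stronger readings are tempting and are not supported:
- **That as-needed use can be seen nowhere else.** Tablets per month, OLE rescue days and OLE triptan or ergotamine days are all planned on other scales. This table is distinctive only in isolating off-days.
- **That the SAP implies 42 dosing days in 28**, by adding a score of 28 to 14 scheduled doses. The SAP never makes that sum, the two terms have different denominators, and the rows without rimegepant do not involve study drug doses.
- **That the true value is always exactly half.** That holds against a calendar rate under strict every-other-day dosing, not against an efficacy-data-day rate with missing diary days.

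**Conclusion.** The measure is wrong as labelled. It is a rate per 28 non-scheduled days presented as days per month. All six rows read about 2.0 times the rate per 28 calendar days, and the attainable maximum is 28 where about 14 non-scheduled days exist. Against an efficacy-data-day rate the factor is 2.0 with complete diaries and 1.8 at an assumed 90% completeness.

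This rests on the every-other-day classification in SAP 7.6.2.3, with few schedule switches, and on the 4-week month. It does not depend on how much medication is taken.

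A reader might infer that the trial's efficacy conclusions or its exposure figures are inflated. They are not: the primary and secondary endpoints, power, Type 1 error and tablet exposure do not use this formula. The consequence is confined to how one descriptive open-label table is read, alone or beside the other monthly measures.

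**What to change.** Either change is sufficient:

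1. Replace the denominator with total efficacy data days through Month 13 in the open-label efficacy period, as for OLE rescue days (6.3.2.2), menstrually-related migraine days (6.3.3.1) and triptan or ergotamine days (6.3.3.3). The result is then on the same scale as those measures, with a maximum of about 14 when diaries are complete. Dividing by all days instead would remove the factor of 2 but would not match them, because days without diary data would count as non-use.
2. Keep the denominator, replace 28 with 100, and label the result as the percentage of non-scheduled days with medication. The assumed subject in the working would show 100 × 26/182 = 14.3%. A footnote should say that non-scheduled days without diary data count as days without use.

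Under option 1, a footnote should also say that the count excludes scheduled days, so that it is not read as total rescue use, which 6.3.2.2 counts over all days.

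The cost is one formula or label and a footnote, with no new data. Under option 1 the reported figures fall to about half with complete diaries, and by less where diary days are missing. If the CSR version of this table used the same scaling, it needs the same note.

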⁵ SAEs, AEs, and Concomitant Procedures must be reported after subject signs informed consent. SAEs should be reported from signing of consent through the 8-week Follow up Safety Visit. Non-serious AEs should be reported from signing of consent through 2-Week Follow up Safety Visit.

⁶ Subjects should finish a bottle of study medication before starting a new bottle. Study drug will be dispensed at monthly (every 4 weeks) study visits, as needed. Unscheduled visits to dispense study medication may be scheduled as needed. Due to the COVID-19 Pandemic, study medication may be shipped to a subject, with up to an 8-week supply. Proper documentation must be maintained in the subject’s source records including shipping vendor, tracking number, confirmation of receipt by subject, and all other relevant information.

⁷ Subjects must take their study medication every other day, regardless of whether or not they have a migraine. During the open-label, extension phase only, if subjects have a migraine on a day that they are not scheduled to take a tablet of study medication, if needed, they may take a study medication tablet to treat a migraine on that calendar day. Therefore, subjects can take a maximum of one (1) tablet of study medication per calendar day. Subjects must report each tablet they take in the eDiary. Doses are not required to be taken in the office on days of a study visit, however dosing requirements and compliance should be discussed with subjects at all visits.

⁸ During the Open-Label, Extension Phase, subjects with 6 or more missed evening reports and 3 or more missed dosing entries per month for 2 months (sequential or non-sequential months) should be considered for discontinuation from the study for poor compliance, after discussion with Sponsor. Month is defined as 4 weeks for the purpose of this protocol.

⁹ The subject will be trained on the use of the eDiary. The subject will use the eDiary every day during the Extension Phase to report migraine occurrence, migraine severity and if the subject treated the migraine.

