### 6.3.2.2 *Rescue Medication Days per Month*

During the DBT and OLE phases, subjects may record taking triptan, ergotamine, and other medications to treat headache or during aura in the eDiary evening report headache log or follow-up headache log.

Rescue medication days per month will be assessed as “rescue medication days per 4 weeks” to correspond with the 4-week visit schedule. Rescue medication days per month are based on data from the previous visit to the current visit (i.e., 4-week interval) where a rescue medication day is defined as a day of efficacy data with complete reference time point date and a “yes” response to at least one of the following questions: taking triptan to treat headache or during aura; taking ergotamine to treat headache or during aura; taking other medication to treat headache.

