### **Rescue Medication Days per Month in the OLE Phase**

Analyses are based on evaluable OL rimegepant mITT subjects with eDiary reference time point dates in the on-OL rimegepant efficacy analysis period.

The number of rescue medication days per month in the OLE phase will be prorated to 28 days and derived as follows:

- Month (i.e., 4-week interval) in the on-OL rimegepant efficacy analysis period:  $28 \times (\text{total number of rescue medication days in the month}) / (\text{total number of efficacy data days in the month})$ . Subjects must have  $\geq 14$  days of efficacy data (not necessarily consecutive) in the specified month to be evaluable.
- Overall OL rimegepant mean:  $28 \times (\text{total number of rescue medication days through Month 13 in the on-OL rimegepant efficacy analysis period}) / (\text{total number of efficacy data days through Month 13 in the on-OL rimegepant efficacy analysis period})$ .

The number of rescue medication days per month in the OLE phase will be summarized descriptively as a continuous parameter (including 2-sided normal 95% CIs for mean) by treatment group and overall in each month of the OLE phase and overall OLE mean.

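### SAP 6.3.3.4 counts open-label non-scheduled days with no headache log as days without rescue use, which biases the rescue rows of a descriptive table downwards

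*SAP*

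**What the plan says.** SAP 6.3.3.4 defines, for each medication category, 28 times the "total number of medication days on the same days as non-scheduled days through Month 13 in the on-OL rimegepant efficacy analysis period" divided by the "total number of non-scheduled days through Month 13 in the on-OL rimegepant efficacy analysis period". It refers to SAP 7.6.2.3 for what a non-scheduled day is and to SAP 6.3.2.2 for rescue medication. The table has six rows, which combine rimegepant, triptan, ergotamine and other rescue medication. It is described as an ad hoc addition to the CSR, later modified for the Addendum Report.

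SAP 7.6.2.3 states: "All days in the on-OL rimegepant efficacy analysis period are classified as either scheduled or non-scheduled days". Days in the planned every-other-day pattern are scheduled; for the rest, "All other days are considered to be non-scheduled days". Its worked example begins "Subject has 26 days in the on-OL rimegepant efficacy analysis period" and classifies each of those days without asking whether a headache log exists.

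SAP 6.3.2.2 is narrower on what can be counted: "a rescue medication day is defined as a day of efficacy data with complete reference time point date", together with a yes answer on triptan, ergotamine or other medication. The overall open-label rescue mean in the same section is divided by the "total number of efficacy data days through Month 13 in the on-OL rimegepant efficacy analysis period". The open-label triptan or ergotamine mean in SAP 6.3.3.3 uses the same denominator.

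**The concern.** The numerator and denominator in 6.3.3.4 are observed on different sets of days. A non-scheduled day with no headache-log entry can never add to a rescue count, but it always adds to the denominator. The formula therefore reads missing as no use. SAP 6.1.1 bases analyses on observed data unless stated otherwise, and 6.3.3.4 states nothing else for rescue use.

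Missed logs are to be expected over 52 weeks. Protocol Table 2, footnote 8, raises discontinuation only for "subjects with 6 or more missed evening reports and 3 or more missed dosing entries per month for 2 months". The evaluable open-label set (SAP section 3) needs 14 diary days in the observation period and in only one open-label month.

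There is also a difference in ascertainment. SAP 7.6.2.3 allows rimegepant doses from the medication reconciliation form to fall on non-scheduled days. The parameters listed for that form in SAP 7.6.2.1 are the missed date and the number of tablets. A reconciled dose on an unlogged day can therefore enter the rimegepant-only row although rescue use that day is unknown.

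What is at stake is the description of acute medication use on days when rimegepant may be taken as needed, and how these rows compare with the open-label rescue and triptan or ergotamine means.

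**Working it through.** **1. The SAP's own example.** Scheduled report dates fall on days 0, 2, 4, 8, 9, 11, 15, 18, 22 and 24 of days 0 to 25. The first is even. Odd gaps occur at day 9 and day 18, so the pattern switches there.
- Scheduled: 0, 2, 4, 6, 8; 9, 11, 13, 15, 17; 18, 20, 22, 24. That is 14 days.
- Non-scheduled: 26 − 14 = 12 days, which matches the SAP's list.

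No diary-completion data enter this count.

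**2. Effect of missing logs in that example.** Assume true rescue use on 4 of the 12 non-scheduled days, and 3 unlogged days, one of them a rescue day (the same one-in-three share).
- Complete diaries: 28 × 4/12 = 9.33.
- 6.3.3.4 formula: 28 × 3/12 = 7.0.
- Logged days only: 28 × 3/9 = 9.33.

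The shortfall is 1 − 7.0/9.33 = 25%, equal to the unlogged fraction 3/12.

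**3. Over 52 weeks.** There are 364/2 = 182 non-scheduled days. Assume rescue use on 2 in 14 of them, unrelated to whether a log was completed. With completion fraction c, the formula gives 28 × (182 × c × 2/14)/182 = 4.0 × c. Dividing by logged days gives 4.0 for any c above zero.

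| Completion on non-scheduled days (assumed) | 6.3.3.4 formula | Logged days only | Relative bias of 6.3.3.4 |
|---|---|---|---|
| 100% | 4.00 | 4.00 | 0 |
| 95% | 3.80 | 4.00 | −5% |
| 23/28 = 0.821 | 3.29 | 4.00 | −18% |
| 22/28 = 0.786 | 3.14 | 4.00 | −21% |

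**4. If missingness is related to use.** Let f be the unlogged fraction and k the rescue rate on unlogged days relative to logged days. Put D = (1 − f) + kf. Then 6.3.3.4/true = (1 − f)/D, and logged-days-only/true = 1/D. With f = 6/28:

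| k | 6.3.3.4/true | Logged days only/true |
|---|---|---|
| 0 | 1.00 | 1.27 |
| 0.5 | 0.88 | 1.12 |
| 1 | 0.79 | 1.00 |
| 2 | 0.65 | 0.82 |

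The 6.3.3.4 ratio is below 1 for every k above 0. For k up to 1 the two relative errors are kf/D (low) and (1 − k)f/D (high), which are equal at k = 0.5. Above 0.5 the logged-day version is the less biased, and below 0.5 the calendar-day version is.

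All rates here are per 28 non-scheduled days, as the formula produces them. Whether that should be called a month is a separate question and does not change the relative bias.

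**The case against.** **The table carries little weight.** It is ad hoc, open-label and descriptive, with no test or model, and none of the exploratory estimands corresponds to it. Open-label rescue and triptan or ergotamine means on efficacy data days are already reported. This stands, and it makes the point minor.

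**The calendar denominator follows another SAP convention.** Average rimegepant exposure is divided by calendar time, and SAP 6.2.6.1 assumes no dose on a day without study drug data. Rimegepant enters four of the six rows. It is therefore wrong to say that every other open-label rate uses diary days. But that assumption is stated for study drug only and does not extend to rescue medication.

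**The period may mean diary days.** SAP 7.4 defines it through reference time point dates. The all-days wording and the 26-day example in 7.6.2.3 point the other way.

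**Restriction may not reduce bias.** If rescue use on unlogged days is less than half that on logged days, the calendar version is closer to the truth. The arithmetic is right. Nothing in the documents suggests such a ratio, but nothing excludes it, which is a reason to show both versions.

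A reader might also infer more than the documents support:
- That the shortfall is always in proportion to missed reports. This needs missingness unrelated to use.
- That losses of 18% or 50% are expected. No open-label completion rate is given. The count of 6 missed reports is one part of a joint trigger, and 14 of 28 days is required in only one open-label month, so it is not a floor for the overall mean.
- That rescue use on a day without its own report is lost for good. Protocol 7.4 allows missing migraine data to be corrected, and SAP 7.6.2.1 dates some log answers back to headache start. A day restored in this way counts as logged and is outside the concern.
- That the table is shown to favour rimegepant. On non-scheduled days rimegepant comes from the logs or the reconciliation form, so a missed and unreconciled log loses both drugs. Any tilt depends on an unknown number of reconciled doses.

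The eDiary compliance tables (SAP 6.2.6.3) show missingness only in part. They count days with any eDiary finding, not headache logs on non-scheduled days.

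**Conclusion.** The concern holds as a minor point. The 6.3.3.4 denominator includes non-scheduled days on which rescue use could not be observed, and the rescue rows are biased down unless no rescue medication was taken on those days. The direction needs no assumption about why logs were missed. The size does: if missingness is unrelated to use, the reported rate is the true rate times log completion on non-scheduled days, which is 5% low at 95% completion and 18% low at 23/28. Both completion rates are assumptions. Misplacement of reconciled doses in the rimegepant-only row is possible but cannot be sized. Primary, secondary and estimand-based exploratory analyses are unaffected.

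**What to change.** In SAP 6.3.3.4, restrict both numerator and denominator to non-scheduled days through Month 13 that have an evening-report or follow-up headache-log entry, i.e. the first clause of the efficacy date definition in SAP 7.3. Efficacy data days as a whole would not be enough, because the second clause admits a non-scheduled day on the strength of a rimegepant date alone, which can come from the reconciliation form.

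Beside the table, report the number of non-scheduled days without a log and the number of reconciled rimegepant doses on them. Keep the calendar-day version as a sensitivity row.

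The cost is a wording change and one program change, with no new data. There are two downsides. Rimegepant doses known only from the reconciliation form leave the main rows, although they remain in the exposure tables. The log-only denominator also differs slightly from that of the open-label rescue and triptan or ergotamine means, which keep the second clause, and a footnote should say so.
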